Psychosocial stressors remain a contributing factor to inadequate sleep,²⁶⁻²⁹ and intervening on stress may result in sleep improvements. Mindfulness-based stress reduction (MBSR) is a evidenced-based intervention that focuses on mindfulness mediation, breathing, and other relaxing methods to reduce negative affect and improve vitality and coping.^{30,31} MBSR is effective at reducing stress levels, ruminative thinking, and anxiety,³² all contributors to poor sleep.³³ Results of a systematic review indicate that increased practice of mindfulness techniques is associated with improved sleep.¹⁷ However more research is needed, particularly regarding the uptake of home practice.³⁴ Furthermore, evidence regarding the uptake of MBSR among populations most-at-risk for inadequate sleep and T2DM is lacking.

[figure not shown]
Hypothesis and Design: Our overarching hypothesis is *that the MBSR intervention will improve sleep quality, extend sleep duration and improve general sleep complaints and that participants who complete the MBSR plus sleep education intervention will have improvements in glucose levels, lipid levels, blood pressure, and biomarkers associated with stress response.*

Project Design: **Population:** The target population is a racially diverse community sample of adults aged 18 years or older who reside in the Atlanta, GA area (N=20). Eligible participants will be proficient in English language, have a iPhone (for the purposes of the application), a sleep quality score ≥ 5 on the validated Pittsburgh Sleep Quality Index³⁵ and prediabetes. We will initially screen for high risk of prediabetes using the American Diabetes Association risk screener.³⁶ Those who are identified as high risk will be confirmed via venous blood test. Prediabetes will be defined as either fasting glucose between 100-125 mg/dL or HbA1c between 5.7-6.4%.³⁷ Participants will be recruited from the community via advertisements, community events and existing community partnerships. Potential participants will be screened by trained research assistants. Eligible participants will be contacted via phone and scheduled to attend a baseline visit to collect a blood sample and attend a sleep education session (see Aim 1). Co-PI, [name] has an extensive experience recruiting from the community and will lead the recruitment strategies.

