history, medications) and a sleep education session. Participants will receive a 1-hour session on sleep hygiene, highlighting the important components of healthy sleep: limiting naps, avoiding stimulants close to bedtime, exercise, establishing a bedtime routine, and optimal sleep environment (e.g. bedroom). [name], Co-PI will deliver the sleep hygiene. At the end of the session, participants will be asked to download the free headspace app (<https://www.headspace.com/headspace-meditation-app>). This app was selected based on the following available features: themed modules, varying meditation techniques, narrator selection, mindful moments, reminders, and journey tracking (i.e., run streaks, time meditated, sessions completed) The app features guided meditations on “Stress and Anxiety” that includes 3 “Basic” courses of 10 sessions each which teach the fundamentals of meditation and mindfulness; 6 themed courses of 10 sessions each such as “managing anxiety” which helps transform anxious thoughts, “letting go of stress” which focuses on reframing negative emotions, “restlessness” which aids in coping with a restless mind, “transforming anger” which emphasizes connecting with our anger and using it to train our minds, “navigating change” which focuses on being comfortable with change, and “reframing loneliness” which aids in feeling more connected to the world. The “Stress and Anxiety” module also features 3 advice sessions on the usefulness of putting down our phones, how to forgive ourselves, and the concept of loneliness. The module additionally features 6 SOS meditation sessions for panic attacks or anxiety, and 8 additional single meditation sessions for unwinding, restoration, stress, frustration, breaks, resetting, fear of flying, and alone time. Participants will undergo short mindfulness exercises daily via the app for 6 weeks. To optimize resources, we will implement the intervention in 4 groups of 5 individuals. Additionally, conducting the intervention in waves will allow us to make adjustments based on participant feedback. Following each wave, there will be a focus group session and blood draw to assess changes in biomarkers from baseline.

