This pilot grant will serve as preliminary data for an NIH R-level application for translational research funding. For example, the National Institute of Diabetes and Digestive Kidney Diseases has an R01 entitled “Translational Research to Improve Diabetes and Obesity Outcomes.” The proposed study will generate the information/knowledge necessary to apply for such a funding mechanism. In particular, the results of the proposed study will help us to determine the needed sample size for the larger study. We will also gain critical feedback regarding the uptake of an app-based intervention. The future study will incorporate the focus-group data to develop a culturally relevant stress reduction intervention, thus allowing us to explore racial/ethnic disparities with the aim of reducing the inequity in diabetes.

PROJECT AS RELATED TO T2DM TRANSLATION RESEARCH

An area of translational research includes the process of applying discoveries generated during laboratory research or in preclinical studies to the development of interventions in target populations. Laboratory studies have shown that sleep deprivation can alter insulin secretion and resistance, and sleep interventions have been shown to improve subclinical markers of diabetes risk. However, these studies have been conducted in predominantly white populations in controlled settings. The aim of this study is to translate these findings into a mindfulness-based stress reduction intervention to improve sleep and subsequently improve subclinical markers for diabetes risk in a diverse sample of adults living in the Atlanta metro area.

COVID PRECAUTIONS

In response to the unprecedented COVID-19 pandemic and the resulting social distancing guidelines, the goals, design, and procedure of this study have changed for the safety of all involved.

Project Goal: The goal of the project is to conduct a pilot study to determine the feasibility of delivering a MBSR plus sleep education intervention to improve sleep and subsequently improve subclinical biomarkers for T2DM risk among a community sample of racially diverse adults (N=20) who are overweight/obese and experience poor sleep quality.

Hypothesis and Design: Our overarching hypothesis is *that the MBSR intervention will improve sleep quality, extend sleep duration and improve general sleep complaints and that participants who complete the MBSR plus sleep education intervention will experience improvements in blood pressure and weight.*

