Project Design: **Population:** Eligible participants will be proficient in the English language, have a iPhone or Android (for the purposes of the application), a sleep quality score >5 on the validated Pittsburgh Sleep Quality Index³⁵ and overweight or obese. Participants will be recruited from the community via social media advertisements and flyer advertisements. Via an online questionnaire, we will screen for overweight or obesity defined by the CDC as a BMI of 25.0 kg/m² or greater⁴¹. Those who are identified as overweight or obese will be contacted and given a blood pressure cuff and scale (RENPHE Digital Bathroom Scale). Consent will be conducted electronically for both participation in the intervention and focus group. Participants will be instructed on how to use both and record their morning weight and blood pressure reading before and after the intervention.

[figure not shown]
Overview: For Aim 1: we propose to deliver sleep education in a virtual group setting, ask participants to install MBSR app on their phones, and monitor sleep patterns using wrist actigraphy for approximately 35 days. The sleep device (Actiwatch), blood pressure cuff, and scales will be delivered to participants without contact. For Aim 2, we will conduct focus groups among participants to determine usability of the app as well as barriers to obtaining optimal sleep. Focus groups will be conducted over the phone/secure video conferencing (i.e. Zoom). For Aim 3, we will analyze changes in weight and blood pressure collected at the start of the study and at follow-up and explore associations between stress, sleep and T2DM biomarkers.

Determine the feasibility of delivering a mindfulness based stress reduction plus sleep education intervention to

improve sleep health: We propose a 4-week MBSR intervention (See Figure 2.1). Questionnaires and sleep hygiene education will be provided over the phone/secure video conferencing (i.e. Zoom). Eligible participants will be provided with a blood pressure cuff, scale, and Actiwatch. Participants will also be remotely instructed by a trained research assistant on how to wear the sleep monitor. No physical contact will be made with participants over the course of the study.

Figure 2.1

Preliminary MBSR Intervention Schedule Overview

Conduct qualitative research to understand the uptake and usability of the mindfulness-based stress reduction intervention for sleep improvement

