Qualitative data will be collected over a series of focus groups that will take place over phone/secure video conferencing (i.e. Zoom).

Assess whether improving sleep through mindfulness-based stress reduction improves subclinical biomarkers associated with T2DM risk

Height and weight will be obtained according to standard procedures. Participants will take their own blood pressure as instructed with an at-home blood pressure monitor given to them. Smoking and alcohol use will be assessed via self-reported questionnaire. Participants will receive a \$50 gift card at baseline, another \$50 at the mid-point check in and a \$100 gift card at follow-up, as well as a detailed health report for their participation at the end of the study.

Data Analysis: Outcome variables will be the mean change in weight and blood pressure. The means of each measure will be compared at baseline and follow up using analysis of variance (ANOVA) tests to assess whether significant changes occurred between pre and post intervention. [name] (Co-PI) has extensive experience in the analysis of biomarkers related to T2DM risk and will conduct all related analyses.

In secondary analyses, we will test cross-sectional associations between sleep measures and subclinical biomarkers for T2DM risk, regardless of intervention adherence. The primary exposures will be average actigraphy defined sleep duration and sleep quality. Secondary sleep outcomes include: night to night standard deviation in sleep duration; sleep efficiency, sleep mid-point (timing; average and standard deviation of night to night differences); sleep debt (weekend-weekday sleep duration), and self-reported quality and daytime functioning (using the PROMIS scale). Sub-clinical outcomes will include mean changes in blood pressure and weight.

Table 1.1 Updated Study Measures and Sources

Sleep	
Sleep diary	Self-completion, home; Facilitates interpretation and assessment of actigraphy
Approx 35-day actigraphy	Identifies sleep/wake times, daytime naps, quality of sleep, sleep timing
Sleep questionnaire	Self-completion; Validated questionnaires to assess sleep duration, sleep quality (Pittsburgh Sleep Quality Index), snoring frequency, in bed activities, self-reported physician-diagnosed sleep disorders, insomnia (Insomnia Severity Index), PROMIS-measure of sleep quality
Psychosocial factors	

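### With no comparator, the pre-post ANOVA of weight and blood pressure cannot support a hypothesis and aim that credit change to MBSR

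*Combined protocol and SAP*

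**What the plan says.** The current design is in the COVID PRECAUTIONS section. Its Project Goal describes one "community sample of racially diverse adults (N=20) who are overweight/obese and experience poor sleep quality". The main section sets out delivery: "we will implement the intervention in 4 groups of 5 individuals". Neither section describes an untreated or alternative group. Everyone receives sleep education and the app.

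The hypothesis in COVID PRECAUTIONS is that "the MBSR intervention will improve sleep quality, extend sleep duration and improve general sleep complaints". Its second half predicts better blood pressure and weight among people who complete MBSR plus sleep education. The Aim 3 heading reads: "Assess whether improving sleep through mindfulness-based stress reduction improves subclinical biomarkers associated with T2DM risk".

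Under that heading, Data Analysis names two outcomes, change in weight and change in blood pressure. It compares baseline with follow-up means by ANOVA "to assess whether significant changes occurred between pre and post intervention". It does not say whether the ANOVA is a repeated-measures one, and it gives no significance level. No pre-post test is specified for PSQI, actigraphy or any other sleep measure; these enter only a secondary analysis of cross-sectional associations.

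Entry requires "a sleep quality score >5 on the validated Pittsburgh Sleep Quality Index". For weight, "we will screen for overweight or obesity defined by the CDC as a BMI of 25.0 kg/m² or greater".

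**The concern.** The hypothesis and Aim 3 are causal and name MBSR. The only before-after analysis is a significance test in a group where everyone is treated. A small p-value would show that weight or blood pressure differed between two dates. It would not show why, and nothing in the plan limits how the result may be read.

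This matters because Future Plans says the pilot will supply preliminary data for a larger grant application and inform its sample size. An uncontrolled change taken as the MBSR effect could make that trial the wrong size.

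**Working it through.** **1. What the contrast contains.** For each outcome the observed mean change is the sum of:
- any MBSR effect;
- any sleep-education effect (the main section places the session at the baseline visit, and the COVID section does not move it);
- time and season;
- growing used to measuring oneself at home;
- expectancy and other effects of taking part.

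That is one estimate for at least five components, so MBSR cannot be isolated. Delivery in waves does not help, because no wave is measured while waiting. The secondary association analysis has no untreated contrast either. The documents give no basis for the size or direction of the non-MBSR components.

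**2. Pairing.** The plan states no power calculation, so there is no figure to reproduce. Let n = 20, let σ be the SD at each occasion and ρ the within-person correlation (0.5 and 0.7 assumed), with two-sided alpha 0.05 assumed.
- The true variance of the mean change is 2σ²(1−ρ)/n. An independent-groups ANOVA uses 2σ²/n, which shrinks the t statistic by √(1−ρ): 0.71 at ρ = 0.5 and 0.55 at ρ = 0.7.
- Simulated type I error is about 0.7% at ρ = 0.5 and 0.1% at ρ = 0.7.
- The paired 95% CI half-width is 2.093/√20 = 0.47 SD of the differences, that is 0.47σ at ρ = 0.5 and 0.47 × √0.6 = 0.36σ at ρ = 0.7. The independent-groups half-width is 2.024 × √(2/20) = 0.64σ.
- A change of 0.66 SD of the differences gives a paired test 80% power. The independent-groups test has about 54% at ρ = 0.5 and 26% at ρ = 0.7 (simulated).

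**3. Regression to the mean in the tested outcomes.** Write λ = φ(z)/(1−Φ(z)), where z is the standardised entry cut-off.
- *Systolic pressure*, selected only through PSQI. Assumed: PSQI mean 6, SD 3, cut-off 5.5; pressure SD 15 mmHg; PSQI-pressure correlation r of 0 to 0.2; PSQI test-retest 0.7 to 0.9; within-person pressure correlation 0.7. Here z = −0.167 and λ = 0.695. The shift is 15 × r × (1 − test-retest) × λ, at most 15 × 0.2 × 0.3 × 0.695 = 0.63 mmHg. The chance of a significant change with no effect is 5.0% to 5.6%.
- *Weight*, selected on BMI. Assumed: BMI mean 29, SD 6.5, test-retest 0.99 to 0.998, height 1.68 m, and screening equal to baseline as the worst case. Here z = −0.615 and λ = 0.452. The shift is at most 0.01 × 6.5 × 0.452 = 0.029 kg/m², and × 1.68² = 0.08 kg. The chance is 5.0% to 5.2%.

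**4. Regression to the mean in PSQI, if the screening score were the baseline.** Assumed: source mean 5 to 7, SD 3 to 3.5, test-retest 0.70 to 0.90. The shift is (1 − test-retest) × SD × λ.
- Smallest (mean 7, SD 3, 0.90): 0.1 × 3 × 0.509 = 0.15 points.
- Largest (mean 5, SD 3.5, 0.70): 0.3 × 3.5 × 0.891 = 0.94 points.
- Simulated paired t-tests with n = 20 and no effect show significant improvement in 7% to 35% of trials. With scores rounded to integers, the fall is 0.17 to 0.95 points and the rate 7.6% to 35.8%. The nominal rate in that direction is 2.5%.
- With a separate baseline PSQI after screening, the rate is 2.4% to 2.7%.

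**The case against.** This is a feasibility pilot. The main section says its chief purpose is process measures, and a lack of attribution is inherent in any single-arm study. The test is also close to nominal size for the two outcomes it covers. All of that stands, and it keeps the point modest. It does not remove it: the causal wording and the significance test are in the plan, no limit on interpretation is, and the results are meant for a grant application.

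A reader might infer something stronger: that the PSQI entry rule makes improvement expected even if MBSR does nothing, so the planned test is biased towards success. The documents do not support this.
- The test covers weight and blood pressure, where step 3 shows almost no such effect.
- PSQI has no planned pre-post test. The key sleep outcomes in the main section come from actigraphy, and self-reported quality in the secondary analyses uses PROMIS.
- Reuse of the screening PSQI is not stated, and the text leans against it. The main section puts screening before a baseline visit at which sleep questionnaires are given. The COVID section screens online and gives questionnaires by phone or video. Its schedule figure is not available here.

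Nor do the documents show that the sponsor would report a significant change as efficacy. The criticism is that the plan as written permits it.

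**Conclusion.** The point holds as one of attribution and analysis. An uncontrolled test of change in weight and blood pressure cannot support the hypothesis or Aim 3 as worded. That follows from the design and needs no assumed figure.

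The loss from ignoring the pairing is conditional, because the plan does not specify the form of ANOVA. Read as independent groups, the test is conservative: type I error is about 0.7% or 0.1% at within-person correlation 0.5 or 0.7, with alpha 0.05 assumed.

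The PSQI figures, a fall of about 0.2 to 1.0 points and significance in roughly 8% to 36% of null trials, rest on assumed population values and on an unstated choice of baseline. They should not be carried over to weight or blood pressure.

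**What to change.** 1. In the COVID PRECAUTIONS Data Analysis, replace the significance test by the mean within-person change in weight and in systolic and diastolic pressure, each with a paired 95% confidence interval.
2. Reword the hypothesis and the Aim 3 heading there to describe change over the study period under the combined app and sleep-education programme. State that this is not evidence that MBSR is efficacious, and that it will not be used as the effect size for the next study. The SD of change, drop-out and adherence can still inform that study.
3. As a minor clarification, state that any reported PSQI change uses the baseline questionnaire given after screening.

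The cost is a revision of wording and a more modest claim. No control arm or extra participants are needed. If a post-screening PSQI is not already planned, it adds one short questionnaire per participant.

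### Aim 3 asks whether improving sleep improves risk markers, but neither stated analysis uses improvement in sleep

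*Combined protocol and SAP*

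**What the plan says.** The current design is in the COVID Precautions section. Its Project Goal is to "improve sleep and subsequently improve subclinical biomarkers for T2DM risk", and the Aim 3 heading is to "Assess whether improving sleep through mindfulness-based stress reduction improves subclinical biomarkers associated with T2DM risk". Its hypothesis adds that "participants who complete the MBSR plus sleep education intervention will experience improvements in blood pressure and weight".

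The Aim 3 Data Analysis text gives two analyses:

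- **Main analysis.** Baseline and follow-up means of weight and blood pressure are compared "using analysis of variance (ANOVA) tests to assess whether significant changes occurred between pre and post intervention". No sleep variable is named.
- **Secondary analysis.** The plan states that "we will test cross-sectional associations between sleep measures and subclinical biomarkers for T2DM risk, regardless of intervention adherence". On exposures: "The primary exposures will be average actigraphy defined sleep duration and sleep quality". Further sleep measures follow: "Secondary sleep outcomes include: night to night standard deviation in sleep duration; sleep efficiency, sleep mid-point", then weekend-weekday sleep debt and self-reported quality and daytime functioning. On outcomes: "Sub-clinical outcomes will include mean changes in blood pressure and weight".

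The Overview in the same section gives about 35 days of actigraphy and says of Aim 3 only that associations among stress, sleep and biomarkers will be explored. The Aim 1 text gives a 4-week intervention. The pre-COVID Aim 3 analysis has the same structure, with blood markers as outcomes.

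**The concern.** The heading and the goal both link improvement in sleep to improvement in markers. The ANOVA can show that weight or blood pressure moved, which answers the hypothesis about completers. It cannot show that the movement went with better sleep.

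The secondary analysis is the only place where the two meet, and it has three faults for this aim:

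- Its exposures are levels, night-to-night variability, a weekend-weekday difference or self-report. None is defined as a change from before to after the intervention.
- It is called cross-sectional although its outcomes are changes over time.
- It does not say which nights are averaged.

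A reader could take a weak or null level association as evidence that sleep gains do not track marker gains. The Future Plans section says the pilot will help set the sample size of a larger study, so a misleading answer could carry forward.

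**Working it through.** **Figures in the plan.** The documents give no power, effect size or standard deviation for this analysis, so there is nothing to reproduce. The point rests on the text. The arithmetic below only illustrates the possible size.

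**A single participant.** Assume 7 pre-intervention and 28 intervention nights (about 35 days, less 4 weeks). Sleep rises from 5 h to 6 h.

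- Immediate gain: (7×5 + 28×6)/35 = 203/35 = 5.80 h.
- Linear gain (k/28 of the gain on intervention night k): the k/28 sum to 14.5, and 5 + 14.5/35 = 5.41 h.

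The 35-night average cannot tell this participant from one who sleeps 5.80 h (or 5.41 h) throughout.

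**Across participants.** Assumed inputs:

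- SD of habitual sleep, sb: 45 or 60 min
- SD of true change, sd: 30 or 40 min
- baseline-change correlation, r: 0 or -0.5
- true correlation of sleep change with marker change: 0.60 (positive = benefit)
- no effect of sleep level other than through its change

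Write the averaged level as A = baseline + w × change. Then

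corr(A, change) = (r·sb·sd + w·sd²) / (sd·√(sb² + w²·sd² + 2·w·r·sb·sd)).

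For the 35-night average with immediate gain, w = 28/35 = 0.80:

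- Highest (sb 45, sd 40, r 0): 32/√(2025 + 1024) = 0.580; ×0.60 = 0.348.
- Lowest (sb 60, sd 30, r -0.5): (-900 + 720)/(30·√(3600 + 576 - 1440)) = -0.115; ×0.60 = -0.069.

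| Nights averaged | Gain | w | The 0.60 appears as |
|---|---|---|---|
| All 35 | immediate | 0.800 | 0.35 to -0.07 |
| All 35 | linear | 14.5/35 = 0.414 | 0.21 to -0.19 |
| Final 7 | immediate | 1.000 | 0.40 to 0.00 |
| Final 7 | linear | 25/28 = 0.893 | 0.37 to -0.04 |
| Baseline 7 | either | 0 | 0.00 to -0.30 |

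**What a change analysis would offer.** With 7-night means and an assumed night-to-night SD, sn, of 60 or 90 min, the observable correlation is 0.60·sd/√(sd² + 2·sn²/7). For sd 30 and sn 60 this is 18/√(900 + 1028.6) = 0.410. Fisher z power at n=20, two-sided 0.05, is Φ(atanh(0.410)·√17 - 1.96) = 0.44. Immediate gain gives 0.27 (sd 30, sn 90) to 0.55 (sd 40, sn 60). For linear gain, multiply sd by 0.893; this gives 0.24 to 0.51.

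**Simulation.** 6,000 trials of 20 participants were run in each of 16 scenarios, counting significant results in the right direction:

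| Analysis | Immediate gain | Linear gain |
|---|---|---|
| Change on change, unadjusted | 27-57% | 24-53% |
| 35-night level | 1-32% | under 1% to 14% |

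**The case against.** The strongest reply is that the hypothesis has two separate parts: sleep improves, and completers' blood pressure and weight improve. It does not say that larger sleep gains bring larger marker gains, so the ANOVA serves the second part and the change analysis is an optional extra. That is a fair reading of the hypothesis. It does not fit the Aim 3 heading, which makes sleep improvement the means.

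Second, the Rationale draws heavily on sleep level and later diabetes, so level against marker change is a coherent question of its own. This stands, and is why the listed exposures should stay. The illustration gives level no effect of its own, and the figures depend on that.

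Third, 0.60 is optimistic. With the same noise inputs, power of the change analysis is about 13-27% at a true correlation of 0.40 and 9-16% at 0.30. This stands, and means the added analysis should be read as an estimate rather than a test.

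Fourth, the sign reverses only when baseline and change are negatively correlated. For the 35-night average with immediate gain, it happens in one of the four SD combinations, below a correlation of -0.40. With linear gain at -0.5 it happens in all four. Positive correlations were not examined.

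Fifth, Table 1.1 lists roughly 35 days of actigraphy, which makes the full record a natural default window. That is likely, but it describes recording, and the analysis text names no window.

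Last, this is a secondary analysis in a single-arm pilot of 20 whose main goals are process measures. That limits the weight of the point without removing it.

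**Conclusion.** The concern holds on the text alone: no stated analysis uses change in sleep as an exposure, the secondary analysis is mislabelled, and its averaging window is open. The general promise to explore associations does not fill the gap.

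Confidence is high for that reading. The magnitudes are conditional on the assumed SDs, the 7 + 28 night split, a true correlation of 0.60 and no separate effect of level. Within them, the planned level analysis recovers at best about 0.35 of the 0.60 with a 35-night average, and can be null or reversed.

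This should be corrected, but it does not affect the feasibility conclusions.

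**What to change.** Keep the listed sleep exposures and add, in substance:

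> Exploratory: change in blood pressure and in weight (follow-up minus baseline) will be related to change in actigraphy sleep duration and, separately, sleep efficiency (mean of the last 7 intervention nights minus mean of the pre-intervention nights). Estimates will be reported with 95% CIs and interpreted as associations.

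Also:

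- State the averaging window for each sleep measure.
- Reserve the term cross-sectional for baseline sleep against baseline blood pressure and weight.
- State that the ANOVA tests pre/post change only.
- Treat adjustment for baseline sleep as an optional sensitivity analysis, because the same noisy baseline week enters both the change score and the covariate. In the simulation with immediate gain, adjusting for baseline sleep and the baseline outcome cost 13-20 points of power at a baseline-change correlation of -0.5 (12-17 from the baseline-sleep term alone) and at most about 4 points at 0.

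**Cost.** Wording only, if pre-intervention nights are recorded, since weight and blood pressure are already taken before and after. The pre-COVID Aim 1 text issues the monitor a week before baseline, and about 35 days against 4 weeks suggests the same now. Figure 2.1 is not shown in the text reviewed, so confirm this from the schedule. If there are no such nights, use the earliest recorded nights as reference, which may understate change, or change in PSQI or PROMIS scores if these are repeated.

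**Limits.** Differences of 7-night means are noisy and n=20 is small: an observed correlation of 0.40 has a 95% CI of tanh(0.424 ± 1.96/√17), about -0.05 to 0.72. Without a control group, the result shows association only.
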